The Royal Women's Hospital [name]

[name] [contact]

Fax:

E-mail: [contact]

PRIMARY SPONSOR CONTACT: [name]

Avipep Pty Ltd [name] [contact]

[contact]

E-mail: [contact]

STUDY MONITOR: Medpace

[name]

> [contact] [contact]

[figure not shown]
E-mail: [contact]

Protocol Synopsis

Title	Phase I Safety and Biodistribution Study of ¹²⁴ I-PEG-AVP0458 Diabody in Patients with TAG-72 Positive Ovarian and Prostate Cancer			
Study Design	Phase I, open-label, single-dose escalation cohort study			
Clinical Sites	1. Austin Health, Heidelberg, VIC			
	2. Peter MacCallum Cancer Centre, Melbourne, VIC			
Investigators	[name], [name], [name], [name], [name], [name], [name]			
Study Drug	PEG-AVP0458 (administered as ¹²⁴ I-PEG-AVP0458)			
Patient Population	TAG-72 positive recurrent or refractory ovarian cancer; advanced			
	prostate cancer; or pre-prostatectomy or pre-radiotherapy primary			
	prostate cancer			
No. Patients	12-18			
Dose groups	Protein dose 1 mg/m ² and 10 mg/m ²			
Radioisotope (tracer)	¹²⁴ I 3-5 mCi			
Mode of Administration	Intravenous			
Regimen	One infusion administered over 1 hour			
Study Objective(s)	Primary objective: to evaluate the safety of PEG-AVP0458 in patients with			
	TAG-72 ovarian and prostate cancer tumours			
	Secondary objectives: to assess biodistribution and tumour uptake,			
	pharmacokinetics (PK), and immunogenicity of ¹²⁴ I-PEG-AVP0458			
Primary Endpoints	Monitoring of incidence and intensity of adverse events (AEs) (graded			
	using NCI CTCAE v4.0) at each study visit			
Secondary Endpoints	a) Biodistribution by PET scans at days 0, 1, 2 or 3, 4 or 5, and 6 or 7			
	b) PK: serum levels of 124 I-PEG-AVP0458 measured by γ counter (blood			
	samples collected on days 0, 1, 2 or 3, 4 or 5, 6 or 7 and 14 (±2);			
	serum levels of PEG-AVP0458 measured by ELISA at all these time			
	points and days 21 and 28 (±2 days)			
	c) Immunogenicity: human anti-diabody antibodies (HADA) levels in			
	serum (blood samples collected at days 0 and then 7, 14, 21, and 28			
	(±2 days)			
Main Inclusion Criteria	TAG-72 positive tumours (ovarian or prostate cancer;			
	immunohistochemistry of archived tumours)			
	Detectable disease deemed likely to be assessable by PET by nuclear			
	medicine physician			
	ECOG Performance status 0-1			
	• Expected survival > 3 months			
	• 18 years or older			

Main Exclusion Criteria	 Undergoing treatment (chemotherapy, immunotherapy or radiation) within 4 weeks of entering this study or planned to receive treatment 		
	within 4 weeks of entering this study of planned to receive treatment within 4 weeks after receiving the study drug		
	Disease-specific criteria		
Study Analyses	Interim analysis after evaluation of the last patient in the second dose		
	level ends		
	Final analysis: at the end of the study		
Study Duration	12 -18 months		
Anticipated Study Start Date	Q1 2012		
Anticipated Enrolment	Q1 2013		
Completion			
Anticipated Study Completion	Q1 2013		

Figure 1. PROTOCOL SCHEMA

- If no patients entered in the 1st dose group experience a dose-limiting toxicity (DLT) (as defined in Section 3.1), then the next dose group may commence 30 days after the last patient on the previous dose group has received the ¹²⁴I-PEG-AVP0458 infusion.
- If any one patient in either cohort of 3 patients experiences a DLT, then 3 additional patients will be entered in that dose group.
- If additional patients are treated in the first dose group, all patients entered must have been observed for 30 days before a new patient may receive an infusion in the second dose group.
- In the event 2 or more patients experience DLT at the first dose level, an additional 3 patients will be entered at a 0.5mg/m² dose level
- Interim analysis will evaluate safety and imaging data available after the dose escalation part of the study and will determine which of the two doses be administered to the last 6 patients in the study. The dose selected will be based on imaging characteristics and pharmacokinetic data of ¹²⁴I-PEG-AVP0458 at each dose level.

TABLE OF CONTENTS

S1	TUDY	PERSONNEL	2
Pı	rotoco	ol Synopsis	6
T/	ABLE (OF CONTENTS	8
A	BBRE\	VIATIONS	12
		ULE OF EVENTS	
1		CKGROUND AND RATIONALE	
	1.1	Ovarian Cancer	
	1.2	Prostate Cancer	
	1.3	AVP0458	
	1.3.1		
	1.	.3.1.1 Expression of TAG-72 in prostate cancer	
	1.	.3.1.2 Expression of TAG-72 in ovarian cancer	18
	1.	.3.1.3 Clinical evaluation of anti-TAG-72 antibodies	18
	1.3.2	2 Antibody based cancer therapy and radioimmunodetection	18
	1.3.3	Recombinant Diabodies	19
	1.3.4	4 AVP0458 Drug Description	19
	1.3.5	Biodistribution of ¹²⁴ I-PEG-AVP0458 in LS174T Xenograft Model	20
	1.4	Rationale for the Study	20
2	STU	JDY OBJECTIVES	20
	2.1	Primary Objective	20
	2.2	Secondary Objectives	20
3	STU	JDY DESIGN	21
	3.1	Summary of Design	21

10.2	2 Ethics Committees	44
11	ADMINISTRATIVE AND LEGAL OBLIGATIONS	44
11.1	1 Protocol Amendments	44
11.2	2 Trial Documentation and Data Storage	45
11.3	3 Data Collection, Management and Quality Assurance	45
11.4	4 Monitoring	46
12	STATEMENT OF CONFIDENTIALITY	46
13	REFERENCES	
	NDICES	

ABBREVIATIONS

%ID/L % injected dose per litre

AE Adverse Event

AIHW Australian Institute for Health and Welfare

ALT Alanine Aminotransferase
AST Aspartate Aminotransferase

AUC Area Under the Curve
BSA Body Surface Area
CA-125 Cancer Antigen 125
CBC Complete Blood Count
CT Computed Tomography

CTCAE Common Terminology Criteria for Adverse Events

DLT Dose-limiting toxicity

DOTA 1,4,7,10-tetraazacyclododecane-1,4,7,10-tetraacetic acid

ECG Electrocardiogram

ECOG Eastern Cooperative Oncology Group

eCRF Electronic Case Report Form(s)

ELISA Enzyme Linked Immunosorbent Assay

FIGO International Federation of Gynaecology and Obstetrics

HADA Human Anti-Diabody Antibody
HREC Human Research Ethics Committee

HSA Human Serum Albumin

lodine radioactive isotope 124

IHC Immunohistochemistry

ITLC Instant Thin-Layer Chromatography

IV Intravenous

LDH Lactate Dehydrogenase mAb Monoclonal antibody

MCH Mean corpuscular haemoglobin

MCHC Mean corpuscular haemoglobin concentration

mCi MilliCurie

MCV Mean corpuscular volume MTD Maximum Tolerated Dose

NCI National Cancer Institute (USA)
PET Positron Emission Tomography

PK Pharmacokinetics

PSA Prostate-Specific Antigen rad Ionizing radiation unit SAE Serious Adverse Event

SAER SAE Report

scFv Single-chain Fv Molecule

SC Subcutaneously

SOP Standard Operating Procedure

SPECT Single Photon Emission Computed Tomography

SSKI Saturated Solution of Potassium Iodide

ULN Upper Limit of Normal

US Ultrasound

USA United States of America

TAG-72 Tumour associated glycoprotein-72

 $\begin{array}{lll} \text{TBR} & \text{Target binding region} \\ \text{TPN} & \text{Total Parenteral Nutrition} \\ \text{TRUS} & \text{Trans-rectal ultrasound} \\ V_{\text{H}} & \text{Variable Heavy (chain)} \\ V_{\text{L}} & \text{Variable Light (chain)} \\ \text{WHO} & \text{World Health Organization} \end{array}$

SCHEDULE OF EVENTS

Activity and Assessments	Screening	Baseline & 124 I-PEG-AVP0458 Diabody Infusion	Post Infusion Assessments		End of Study				
Day in cycle	-21 to -1	0	1	2 or 3	4 or 5	6 or 7	14 (±2)	21 (±2)	28 (±2)
Visit Number	Screening ¹	Baseline	Visit 1	Visit 2	Visit 3	Visit 4	Visit 5	Visit 6	End of Study Visit 7
PROCEDURE									
Informed Consent*	X								
Immunohistochemistry for TAG-72 in									
archived tissue samples ²	X								
CT scan ¹²	X								
Inclusion/Exclusion Criteria (eligibility)	X								
Demographics	X								
Medical history	Х								
Serum Pregnancy Test ³	Х								
Thyroid Function Levels (TSH)	Х								X
Vital Signs ⁴	X	X	Х	Х	Х	Х	Х	Х	X
Physical Examination	Х								Х
ECOG Performance	Х	Х	Х	Х	Х	Х	Х	Х	Х
12 Lead Electrocardiogram	X						Х		Х
CBC and differential ⁵	Х						Х		Х
Serum biochemistry ⁶	X						Х		X
PSA or CA-125	X								
¹²⁴ I-PEG-AVP0458 Diabody Infusion		Х							
AE Assessment ⁷		Х	Х	Х	Х	Х	Х	Х	Х
Concomitant medications ⁸	X	Х	Х	Х	Х	Х	Х	Х	Х
SSKI administration ⁹		Х	Х	Х	Х	Х			
Blood for HADA		Х				Х	Х	Х	Х
Blood for PK (protein)		X ¹⁰	Х	Х	Х	Х	Х	Х	Х
Blood for ¹²⁴ I counting		X ¹⁰	Х	Х	Х	Х	Х		
PET Imaging		X ¹¹	Х	Х	Х	Х			
Total volume of blood drawn	15	55	10	10	10	15	30	10	25
(cumulative total [mL])	(15)	(70)	(80)	(90)	(100)	(115)	(145)	(155)	(180)

SCHEDULE OF EVENTS (continued)

- 1) These tests can be done up to 21 days prior to initiating the study.
- 2) Immunohistochemistry for TAG-72 expression in archived tissue samples may be performed at any time prior to initiating the study, using methods outlined in Section 4.4.
- 3) For women of childbearing potential.
- 4) Vital Signs: blood pressure, pulse, respiration and temperature. On day of infusion (Day 0), vital signs are taken at baseline prior to infusion, every 15 minutes during the infusion, and at completion of infusion, and at 1, 2 and 4 hours post infusion completion.
- 5) CBC and differential: Haemoglobin, erythrocytes, platelet count, leukocytes, absolute neutrophil count, eosinophils, lymphocytes, basophils, monocytes, MCV, MCH, MCHC
- 6) Biochemistry: Electrolytes, urea, creatinine, alkaline phosphatase, bilirubin, albumin, AST, ALT, LDH, calcium, phosphate obtained at baseline. Biochemistries repeated as per Schedule of Events. Measure prostate specific antigen (PSA) in patients with prostate cancer and CA-125 in patients with ovarian cancer at Screening only.
- 7) AE Assessment: All AEs, serious and non-serious, will be fully documented on the electronic case report form (eCRF) during the study phase.
- 8) Concomitant therapies: prescription and non-prescription therapies must be documented on the eCRF at each visit. Trade or generic name, indication, quantity administered, route, and dates of administration will be listed. Treatment history will include the 4 weeks prior to the first infusion of ¹²⁴I-PEG-AVP0458.
- 9) Super-saturated potassium iodine (SSKI): 10 drops orally twice a day for 10 days, commencing prior to infusion of ¹²⁴I-PEG-AVP0458.
- 10) On day 0, before infusion, at completion of infusion, and at 1, 2, and 4 hours after completing infusion.
- 11) PET Scan: approximately 1 hour after infusion on day 0.
- 12) CT scan: may be done up to 28 days prior to initiating the study.

^{*} Participants must give consent in writing prior to screening and only after a complete written and verbal explanation of the study has been given to the participant.

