4.3.1 Ovarian Cancer

- Disease-specific exclusions
 - Evidence of current complete or partial bowel obstruction
 - Need for IV or TPN hydration
- Chemotherapy, immunotherapy, biologic therapy, radiation therapy, or other investigational product within 4 weeks prior to study entry or likely to be required during the 4-week onstudy period
- Patients using corticosteroids or immunosuppressive agents: low dose oral corticosteroids for concomitant medical conditions are permitted. Inhaled or topical corticosteroids are permitted.
- Patients with active infections requiring antibiotics, with bleeding disorders or with other serious illness
- Women who are pregnant (positive hCG test) or lactating
- Women of child-bearing potential who are unwilling to utilize a medically acceptable method of contraception
- Patients with a concurrent active serious medical condition likely to affect participation in the study, such as a documented myocardial infarction ≤3 months prior to screening or unstable angina pectoris.
- Patients unable to sign informed consent or unwilling to comply with the procedural requirements of this clinical protocol.

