5.1.3 All other Screening (Day -21 to -1)

Patients who meet the inclusion criteria for TAG-72 tumour expression will undergo further screening as follows:

- Complete medical history including demographics.
- Complete physical examination
- Vital signs (blood pressure, pulse, respiratory and temperature)
- ECOG (Eastern Cooperative Oncology Group) performance
- 12-lead electrocardiogram
- Full blood profile (CBC and differential)
- Serum biochemistry (electrolytes, urea, creatinine, alkaline phosphatase, bilirubin, albumin, AST, ALT, LDH, calcium, phosphate) and thyroid function levels (TSH)
- Prostate specific antigen (PSA) levels in patients with prostate cancer and CA-125 levels in patients with ovarian cancer.
- Serum pregnancy test for women of child bearing potential
- Concomitant medications. Prescription and non-prescription therapies must be documented. Trade or generic name, indication, quantity administered, route, and dates of administration will be listed. Treatment history will include the 4 weeks prior to the infusion of ¹²⁴I-PEG-AVP0458.

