5.2 Baseline prior to Administration of Investigational Product (Day0)

Subjects will attend the study site (Austin Health or Peter MacCallum Cancer Centre) by approximately 8 am.

The following assessments and activities will be undertaken:

- Vital signs (blood pressure, pulse, respiratory and temperature)
- ECOG performance
- Concomitant medications. Prescription and non-prescription therapies must be documented. Trade or generic name, indication, quantity administered, route, and dates of administration will be listed.
- Blood sample taken before infusion of ¹²⁴I-PEG-AVP0458 for assessment of HADA and pharmacokinetics by ELISA and ¹²⁴I counting.
- Administer 10 drops super saturated potassium iodide (SSKI) immediately prior to infusion of ¹²⁴I-PEG-AVP0458 (and twice daily for a total of 10 days).

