5.9 Safety Monitoring and Management

5.9.1 Infusion Safety Monitoring

On the day of ¹²⁴I-PEG-AVP0458 infusion, all patients will have baseline vital signs taken prior to the infusion. Saturated solution of Potassium Iodide (SSKI) (obtained from Hospital pharmacy), 10 drops twice daily, will be administered immediately prior to the infusion and will continue for a total of 10 days. All concomitant therapies and ongoing AEs occurring since the last visit will be reviewed and documented in the patient's medical history and eCRF.

For the infusion, vital signs and careful monitoring for symptoms such as allergic reactions will be measured and recorded during the infusion and the 4 hours post infusion completion. Vital signs and all AEs occurring during this period will be documented in the patient's medical history and eCRF.

All Grade 2 and higher AEs occurring during the infusion and up to 4 hours post-infusion are considered to be infusional toxicities regardless of relationship to drug and CTCAE v4.0 Grade.

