5.14 Criteria and rules for stopping patient treatment

An Investigator may stop a patient's participation for the following reasons:

- The patient withdraws consent.
- The patient is no longer able to participate.
- A patient can be withdrawn after discussion between the Sponsor and Investigator if eligibility criteria are violated or if the patient fails to comply with the protocol (e.g., nonadherence to study assessment visits).
- The Investigator's judgment that continued participation is no longer in the patient's interest.

Documentation of the details of withdrawal will be included in the eCRF. All patients who receive the ¹²⁴I-PEG-AVP0458 infusion will be evaluated for safety.

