7.2.3 Pregnancy Reporting

Any pregnancy that occurs in a study subject or his partner during the study or occurring up to 30 days after the last dose of study medication must be reported. Study site personnel must complete and fax the Exposure in Utero form within one working day to Medpace Clinical Safety [contact].

Follow-up should be documented in source notes and should be continued until final outcome is known. Study site personnel must complete and fax the follow-up Exposure in Utero form to Medpace Clinical Safety when new information or the final outcome of the pregnancy is available.

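### The only scheduled pregnancy test may be up to 21 days old at the ¹²⁴I-PEG-AVP0458 infusion, and no Day 0 step in the protocol repeats or confirms it

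*Protocol*

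**What the plan says.** The exclusion criteria for ovarian cancer (4.3.1) rule out "Women who are pregnant (positive hCG test) or lactating" and also "Women of child-bearing potential who are unwilling to utilize a medically acceptable method of contraception".

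The test that supports the first exclusion appears in two places. Section 5.1.3, whose window is Day -21 to -1, lists "Serum pregnancy test for women of child bearing potential". The Schedule of Events has one mark in the Serum Pregnancy Test row, in the Screening column. Footnote 3 limits it to women of childbearing potential, and footnote 1 sets the timing of the screening tests: "These tests can be done up to 21 days prior to initiating the study". The inclusion/exclusion row is also marked at Screening only.

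On Day 0 before infusion, 5.2 asks for vital signs, ECOG status, concomitant medications, blood for HADA and PK, and SSKI. Section 5.9.1 states that "all patients will have baseline vital signs taken prior to the infusion", and adds SSKI and a review of concomitant therapies and ongoing adverse events. Neither mentions pregnancy.

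Two later provisions bear on the point. Section 5.14 says: "A patient can be withdrawn after discussion between the Sponsor and Investigator if eligibility criteria are violated". Section 7.2.3 requires a report of "Any pregnancy that occurs in a study subject or his partner during the study" and for 30 days after the last dose.

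**The concern.** A pregnancy exclusion protects only if pregnancy status is known at the time of exposure. Here the exposure is one infusion that cannot be withdrawn: 3-5 mCi of ¹²⁴I attached to a protein not previously given to humans. The schedule allows up to three weeks between the only test and that infusion. A woman could test negative on Day -21, have a pregnancy that started or became detectable afterwards, and be infused on Day 0 without any departure from the protocol.

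The stake is participant safety. The primary endpoint, the sample size and the DLT rule do not depend on it.

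**Working it through.** **Age of the result at infusion.** Inputs: the screening window Day -21 to -1 (Schedule of Events and 5.1.3) and infusion on Day 0.

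- Age = infusion day minus test day.
- Shortest: 0 - (-1) = 1 day.
- Longest: 0 - (-21) = 21 days.

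Footnote 1 counts back from the start of the study, not from infusion. The column heading and 5.1.3 fix the window relative to Day 0, so the figure of 21 days stands.

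**Is a Day 0 test implied by the blood volumes?** Inputs: five Day 0 PK samples (footnote 10: before infusion, at completion, and 1, 2 and 4 hours later); 10 mL per PK time point (6.3); the stated totals of 10 mL at Visit 3, 15 mL at Visit 4 and 55 mL on Day 0.

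- PK: 5 × 10 = 50 mL.
- HADA: Visit 4 adds only HADA to the blood tests of Visit 3, so 15 - 10 = 5 mL.
- Sum: 50 + 5 = 55 mL, which reproduces the stated Day 0 total.
- Left for a serum hCG sample: 55 - 55 = 0 mL.

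This agrees with the empty Day 0 cell in the pregnancy-test row. It does not rule out a urine test, but none is listed.

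**Do other provisions detect a pregnancy before infusion?**

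| Provision | What it does | Detects before infusion? |
|---|---|---|
| 4.3.1, contraception criterion | Lowers the chance of pregnancy | No |
| Eligibility row | Marked at Screening only | Not after Screening |
| 5.2 and 5.9.1, Day 0 steps | No hCG test or check of the result | No |
| 5.14, withdrawal | Acts on a violation already recognised | No |
| 7.2.3, reporting | Acts once a pregnancy is known | No |

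**Effect of a mandatory repeat on the oldest permitted result.** The time limit is an assumption, because the protocol gives none.

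| Repeat required within | Oldest result at infusion | Reduction from 21 days |
|---|---|---|
| 24 hours | 1 day | 20 days |
| 72 hours | 3 days | 18 days |
| 7 days | 7 days | 14 days |

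**The case against.** The strongest reply is that this is a preference and not an error. The exclusion and the window do not contradict each other, the document offers no standard by which 21 days is too long, and any tighter limit is the reviewer's choice. It is true that there is no contradiction and that 72 hours is assumed. The case rests on what the schedule permits when followed exactly.

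Second, the group at risk may be empty. Only ovarian cancer patients are concerned. They must have relapsed or refractory disease with detectable metastases (4.2.1), and section 1.1 describes surgery followed by combination chemotherapy as the usual course. Only 3 of the planned 12 patients must have ovarian cancer (3.2, second part). Harm also requires a contraceptive failure within a narrow period. This stands and limits the size of the point. However, 4.2.1 admits women from age 18 and requires neither menopause nor surgical sterility, and the protocol itself provides for women of child-bearing potential.

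Third, the PET Imaging Charter or the sites' radiotracer procedures may include a pregnancy check. They are not available, so the point is confined to the protocol text. Section 5.2 does not refer to them for this purpose.

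Finally, a repeat test can still miss a very early pregnancy. That is correct: it shortens the unchecked interval but does not remove it.

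**Conclusion.** The point holds as a modest safety gap in the schedule. The only pregnancy test required by the protocol can be 1 to 21 days old at infusion, and no Day 0 step repeats or confirms it. The dates follow directly from the document. Two things are not known: how many women of child-bearing potential would enrol, which is probably few and may be none, and whether procedures outside the protocol already include a check. No probability of an exposed pregnancy can be calculated from the document. It merits consideration because the exposure is irreversible and the remedy is cheap.

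**What to change.** Keep the screening serum test and add a mandatory repeat:

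1. **Schedule of Events, Serum Pregnancy Test row and footnote 3.** Suggested text: *For women of childbearing potential: at Screening, and repeat hCG test within 72 hours before infusion, with the result known before radiolabelling on the morning of Day 0.* The 72 hours is a proposal for the investigators and ethics committees to confirm. Tying the result to radiolabelling (9.2) avoids preparing a dose that cannot be given.
2. **Section 5.2.** Add: *Women of child-bearing potential: confirm negative repeat hCG result before infusion.*
3. **Blood-volume row.** If the repeat is a serum test, add its volume for these women.

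The cost is wording in the Schedule of Events and 5.2, with ethics committee approval of the amendment. Each woman concerned has one extra test (a blood draw if it is done on serum) and possibly one extra attendance, because no visit is scheduled between Screening and Day 0. Women whose screening test already falls within the chosen limit could be exempted from the repeat, if the wording says so.

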1 BACKGROUND AND RATIONALE

1.1 Ovarian Cancer

Ovarian cancer is the most common cause of death due to gynaecological cancers in developed countries. In Australia, a total of 1,226 ovarian cancer cases were diagnosed and 795 deaths from ovarian cancer were recorded in 2006 [1]. In the United States of America (USA), an estimated 21,550 new cases were diagnosed and 14,600 women died in 2009 [2]. The major reason for this high morbidity is that at least 75% of patients are diagnosed when disease is already in advanced metastatic stages.

According to the differentiation stage of the tumours, approximately 90% of primary malignant ovarian tumours are epithelial (carcinomas). The four major types of epithelial tumours are: serous, endometrioid, clear cell, and mucinous. In addition to type of differentiation, ovarian carcinomas can be sub-classified based on degree of differentiation (tumour grade). The International Federation of Gynaecology and Obstetrics (FIGO) grading system uses 3 grades, based on architectural criteria, such as the proportion of glandular or papillary structures relative to areas of solid tumour growth. Grades 1, 2, and 3 correspond to <5%, 5–50%, and >50% solid growth, respectively.

Patients with metastatic ovarian cancer undergo surgery as initial therapy, but most of them cannot be cured by surgery alone due to residual peritoneal disease. Because ovarian cancer is a chemosensitive disease and numerous chemotherapeutic agents have been shown to produce objective responses following surgery, patients are placed on combination chemotherapy after surgery. Although about 75% of all patients with advanced ovarian cancer reach clinical complete remission, median progression-free survival ranges from 16 to 21 months, depending on the volume of disease at the time chemotherapy was initiated [3].

